2. OBJECTIVES AND ENDPOINTS

Primary objective:

To determine the frequency and timing of folate deficiency in patients with solid tumors harboring molecular alterations such as germline and somatic mutations in *BRCA1* and *BRCA2* genes, other genes in Homologous DNA Recombination Repair (HRR) pathway, genomic stability as determined by Homologous Recombination Deficiency (HRD) assay, etc., who are treated with olaparib.

Secondary objectives:

To evaluate the effect of folic acid supplementation on serum folate, hemoglobin level, transfusion needs/number of transfusions, and need for olaparib treatment interruption, dose reduction and drug discontinuation.

To assess response rate (RR) to olaparib as it relates to serum folate level and folic acid supplementation.

Clinical Study Protocol - 6
Olaparib - ESR-18-13807

To assess progression-free survival (PFS) as it relates to serum folate level and folic acid supplementation.

Exploratory objectives:

To elucidate the mechanism of folate deficiency in patients treated with olaparib including possible interaction with germline *BRCA1* and *BRCA2* mutations via testing for folate receptors using immunohistochemistry on available paraffin embedded tumor samples from enrolled patients.

Primary endpoint:

The primary binary endpoint of the study is the percentage of patients who develop drug-induced folate deficiency, defined as serum folate level <7 ng/mL, within three months from start of olaparib therapy.

Secondary endpoints:

To assess the impact of folic acid supplementation on anemia, need for transfusion, and olaparib treatment interruption, dose reduction and drug discontinuation as compared to those who did not receive/require folic acid supplementation

To determine tumor response rate (RR), using treating physician assessment, on olaparib therapy in patients who develop folate deficiency and receive folic acid supplementation as compared to those who do not receive/require folic acid supplementation. Will also compare RR to historical controls (patients with solid tumors treated with olaparib or other approved agents on clinical trials).

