4.2 Exclusion criteria

Medical conditions

1. Patients with folic acid deficiency, defined as folate <7 ng/mL, or those taking folic acid supplementation within 30 days of olaparib initiation.
2. Other malignancy unless curatively treated with no evidence of disease for ≥ 5 years except: adequately treated non-melanoma skin cancer, curatively treated in situ cancer of the cervix, ductal carcinoma in situ (DCIS), Stage 1, grade 1 endometrial carcinoma. Patients with a history of localised triple negative breast cancer may be eligible, provided they completed their adjuvant chemotherapy more than three years prior to registration, and that the patient remains free of recurrent or metastatic disease
3. Persistent toxicities (>Common Terminology Criteria for Adverse Event (CTCAE) grade 2) caused by previous cancer therapy, excluding alopecia.
4. Patients with myelodysplastic syndrome/acute myeloid leukaemia or with features suggestive of MDS/AML.

Clinical Study Protocol - 6
Olaparib - ESR-18-13807

5. Patients with symptomatic uncontrolled brain metastases. A scan to confirm the absence of brain metastases is not required. The patient can receive a stable dose of corticosteroids before and during the study as long as these were started at least 4 weeks prior to treatment. Patients with spinal cord compression unless considered to have received definitive treatment for this and evidence of clinically stable disease for 28 days.
6. Patients considered a poor medical risk due to a serious, uncontrolled medical disorder, non-malignant systemic disease or active, uncontrolled infection. Examples include, but are not limited to, uncontrolled ventricular arrhythmia, recent (within 3 months) myocardial infarction, uncontrolled major seizure disorder, unstable spinal cord compression, superior vena cava syndrome, extensive interstitial bilateral lung disease on High Resolution Computed Tomography (HRCT) scan or any psychiatric disorder that prohibits obtaining informed consent.
7. Patients unable to swallow orally administered medication and patients with gastrointestinal disorders likely to interfere with absorption of the study medication.
8. Immunocompromised patients, e.g., patients who are known to be serologically positive for human immunodeficiency virus (HIV).
9. Patients with known active hepatitis (i.e. Hepatitis B or C).

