5.5 Concomitant therapy

The use of any natural/herbal products or other traditional remedies should be discouraged, but use of these products, as well as any medication or vaccine including over-the-counter or prescription medicines, vitamins, and/or herbal supplements that the patient is receiving at the time of enrolment or receives during the study must be recorded along with:

- Reason for use
- Dates of administration including start and end dates
- Dosage information including dose and frequency

The information on vitamin intake will be collected at the baseline and throughout the duration of the study. Patients will be discouraged to take folate-containing vitamin supplements for at least three months after starting olaparib therapy. However, if they have been on them before the enrolment and decline holding them, they are still eligible to participate.

Anti-emetics/Anti-diarrheals

From screening onwards, should a patient develop nausea, vomiting and / or diarrhea, then these symptoms should be reported as AEs (see Section 8.3) and appropriate treatment of the event given.

Medications that may NOT be administered

Table 2 Prohibited medications

Prohibited medication/class of drug:	
Anticancer therapy:	Not permitted while the patient is receiving study medication
Chemotherapy	
Immunotherapy	
Radiotherapy (except palliative)	
Biological therapy	
Other novel agents	

*Hormone Replacement Therapy (HRT) is acceptable

Clinical Study Protocol - 6
 Olaparib - ESR-18-13807

*Anti-hormonal agents such as aromatase inhibitors are acceptable.

Restricted concomitant medications

Table 3 Restricted concomitant medications

Medication/class of drug:	Usage (including limits for duration permitted and special situations in which it’s allowed):

Strong CYP3A inhibitors:
 
itraconazole, telithromycin, clarithromycin, boosted protease inhibitors, indinavir, saquinavir, nelfinavir, boceprevir, telaprevir
	
Strong or moderate CYP3A inhibitors should not be taken with olaparib. If there is no suitable alternative concomitant medication then the dose of olaparib should be reduced for the period of concomitant administration. The dose reduction of olaparib should be recorded in the CRF with the reason documented as concomitant CYP3A inhibitor use.

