8.2 Sample size determination

A previous study by Rush investigators observed folate deficiency (<7 ng/mL) in 66% of patients treated with olaparib. A sample size of $n=60$ is calculated using one-sided test to have 80% power in detecting more than half (50%) of the patients having folate deficiency at 0.05 significance level. Allowing for 20% attrition, we propose a sample size of $n=75$ for this study.

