8.3 Populations for analyses

Clinical Study Protocol - 6
Olaparib - ESR-18-13807

All enrolled patients who receive at least one dose of olaparib will be included in the analysis population to be used to assess the efficacy and safety endpoints.

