8.4 Statistical analyses

8.4.1 Efficacy analyses

Patients will be monitored for development of anemia and folate deficiency at scheduled time points throughout the course of the study, as described in Section 1.1. Patients who develop \leq G2 cytopenias and folate deficiency will be randomly assigned in a 1:1 ratio to receive folic acid supplementation 1 mg daily or no supplementation. Patients who develop G3 or higher cytopenias and folate deficiency will be started on folic acid supplementation, thus not included in the randomization. For patients who are randomized, we will assess the impact of folic acid supplementation on anemia, need for transfusion, and dose interruption, dose reduction and drug discontinuation of olaparib as compared to those who did not receive/require folic acid supplementation. Additionally, PFS and RR to olaparib will be compared amongst randomized patients relative to folic acid supplementation.

The statistical analysis will provide descriptive summaries as well as 95% confidence intervals for the primary endpoint of drug-induced folate deficiency in addition to response rate and other secondary endpoints. Kaplan-Meier methodology will be used to estimate the PFS curve and estimate of median PFS and corresponding 95% confidence interval will be provided. The significance of the observed percentage of folate-deficient cases will be assessed by statistical hypothesis test, as well as by multivariable analysis of the binary endpoint of folate deficiency adjusted by important covariates. Covariates will include age, race/ethnic group, previous therapy, Hgb prior to olaparib therapy, genetic testing result (*BRCA* carrier status). RR and PFS will be compared to historical controls as a descriptive comparison. Analyses will be reported on the entire combined cohort of patients with solid tumors and also separately for each cancer type. The statistical analysis of the exploratory endpoint will be specified in the SAP. Statistical analysis will be performed in the R Statistical software. No adjustment for multiplicity will be made.

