8.5 Interim analyses

We consider would be reasonable to initially accrue 30 patients and re-evaluate the need for continued accrual based on the percentage of patients who develop folate deficiency in this first phase.

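### Sections 4.2 and 5.5 overlap on patients who take folate-containing vitamins; section 8.3 counts them in the primary test, and no analysis accounts for their folate intake

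*Combined protocol and SAP*

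**What the plan says.** All references are to the combined protocol and SAP.

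- Section 4.2, exclusion item 1, excludes patients with baseline folate below 7 ng/mL and "those taking folic acid supplementation within 30 days of olaparib initiation".
- Section 5.5 takes a softer line on vitamins: "Patients will be discouraged to take folate-containing vitamin supplements for at least three months after starting olaparib therapy". It then adds: "However, if they have been on them before the enrolment and decline holding them, they are still eligible to participate". Vitamin intake is to be recorded at baseline and throughout, with dose and dates.
- Section 2 defines the primary endpoint as serum folate below 7 ng/mL "within three months from start of olaparib therapy", the same length of time for which section 5.5 discourages vitamins.
- Section 8.2 sizes the trial for "80% power in detecting more than half (50%) of the patients having folate deficiency at 0.05 significance level", one-sided, from an earlier observed rate of 66%. That gives 60 evaluable patients, or 75 after 20% attrition.
- Section 8.3: "All enrolled patients who receive at least one dose of olaparib will be included in the analysis population".
- Section 8.4.1, on the multivariable analysis: "Covariates will include age, race/ethnic group, previous therapy, Hgb prior to olaparib therapy, genetic testing result" (the last meaning BRCA carrier status). Folate intake is not on the list.
- Section 8.5 re-evaluates accrual after 30 patients "based on the percentage of patients who develop folate deficiency in this first phase".

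**The concern.** The two eligibility texts use different terms, one for folic acid supplements and one for vitamins that contain folate, and neither is defined by product or dose. A patient whose daily vitamin contains folic acid fits both. In a multi-center study nothing in the text stops two sites from deciding differently about the same kind of patient.

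The statistical consequence comes from what follows enrolment. The trial asks how often olaparib is accompanied by low folate. A patient who keeps taking folate during the three-month window may stay above 7 ng/mL for that reason. The protocol itself treats outside folate as relevant: it discourages it for that period, and it uses folic acid to treat deficiency. Yet the analysis pools users and non-users and never uses the recorded intake. If folate protects some users, the pooled percentage understates the rate among patients without outside folate, the test against 50% loses power, and the 30-patient decision rests on the same diluted figure.

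**Working it through.** **Inputs from the documents.** Null rate 0.50, alternative 0.66, one-sided alpha 0.05, power 80%, 60 evaluable patients, 20% attrition (section 8.2).

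**Inputs assumed.** The share of continuing vitamin users (5%, 10%, 20%) and their deficiency rate q (0, 33%, 50%, 66%). The documents give neither. I also assume that 66% applies to non-users; the documents do not say whether the earlier cohort took vitamins.

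**Step 1: reproduce the plan.** Normal approximation:

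n = [(1.645 × √(0.5 × 0.5) + 0.842 × √(0.66 × 0.34)) / 0.16]² = 58.2, so 59.

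Using the null variance throughout gives 60.4. The exact binomial test with 60 patients rejects at 37 or more deficient, with size 0.046 and power 0.802 at 66%. Attrition: 60 / 0.8 = 75. The plan's figures hold.

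**Step 2: count users, as section 8.3 does.** With u users among the 60, the number deficient is Bin(60 − u, 0.66) + Bin(u, q). Power is the probability that this sum is at least 37. The expected overall rate is [(60 − u) × 0.66 + u × q] / 60; for u = 6 and q = 0.33 it is (35.64 + 1.98) / 60 = 62.7%.

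| Users among 60 | q = 0 | q = 33% | q = 50% | q = 66% |
|---|---|---|---|---|
| 3 (5%) | 63% | 72% | 76% | 80% |
| 6 (10%) | 41% | 62% | 72% | 80% |
| 12 (20%) | 7% | 41% | 63% | 80% |

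**Step 3: leave users out, without replacement.** Exact test on non-users at 66%:

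| Non-users | Reject at | Size | Power |
|---|---|---|---|
| 57 | 36 | 0.031 | 73% |
| 54 | 34 | 0.038 | 73% |
| 48 | 31 | 0.030 | 65% |

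The 57 and 54 rows give the same rounded power because the exact test moves in whole patients and its size differs.

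**Step 4: compare the two.** Leaving users out raises power when few of them become deficient (10% users, q = 33%: 62% to 73%). It is close to neutral at q = 50% (76%, 72% and 63% counted, against 73%, 73% and 65% left out). It costs power at q = 66% (80% down to 73%, 73% or 65%). Neither population is better throughout, so the case is for showing both.

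**Step 5: the 30-patient review.** With 3 users at q = 33%, the expected count is 27 × 0.66 + 3 × 0.33 = 18.8 of 30 (62.7%), against 19.8 (66%) with no users. Section 8.5 sets no threshold, so the effect on that decision cannot be computed.

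**The case against.** The strongest reply is that the texts can be reconciled. Section 5.5 addresses this very patient and admits them, and a specific sentence can govern a general one. Elsewhere the protocol uses folic acid supplementation for the 1 mg study treatment, so exclusion item 1 may mean stand-alone folic acid only. Section 4 and exclusion item 11 also allow exceptions. This is a fair reading, and it makes the matter one of drafting, but the protocol does not state it. On every such reading the users are enrolled, so the analysis question remains.

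Second, counting users is defensible. This is a pilot study of how often deficiency occurs in olaparib-treated patients, some of whom take vitamins. Dilution works against claiming more than 50%, so it adds no false-positive risk. Both points stand, and they are why the section 8.3 population should remain primary. They do not explain why recorded intake goes unused.

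Three stronger readings are tempting, and the documents do not support them:

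- *That the plan has no rule on whether users count.* It has one: section 8.3 includes everyone with at least one olaparib dose. What is missing is any analysis that accounts for their intake.
- *That power collapses to 41% or 7%.* Those figures need 10% or 20% users and not one of them deficient. The protocol itself expects deficiency to persist on 1 mg of folic acid in some patients, since sections 1.1, 3.1 and 5.6 allow 2 mg or more. Zero is an extreme bound, and no vitamin dose is given from which to judge protection.
- *That users should be removed from the primary test and replaced.* Keeping 60 evaluable non-users would need 60 / (0.8 × 0.95) = 79, 60 / (0.8 × 0.90) = 84 or 60 / (0.8 × 0.80) = 94 patients for 5%, 10% or 20% users. Step 4 shows that removal without replacement gains little or loses power once about half of users become deficient.

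**Conclusion.** The point holds as a minor one, with medium confidence. Sections 4.2 and 5.5 overlap with no dividing line. Patients with continuing folate intake enter the primary percentage by default, and no planned analysis would show whether they changed it. The text alone establishes this.

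The size is conditional. If 5% to 10% of the 60 evaluable patients are continuing users and 33% of them become deficient, exact power falls from 80% to 72% and 62% respectively. If users become deficient as often as others, nothing is lost. The user share, their rate, and the application of 66% to non-users are all assumptions. The plan's sample size contains no arithmetic error.

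**What to change.** 1. Make exclusion item 1 and section 5.5 state one rule. For example, exclusion item 1 covers stand-alone folic acid, and other folate-containing vitamins are allowed and recorded.
2. Keep the section 8.3 population for the primary test.
3. In section 8.4.1, prespecify that the primary percentage and its 95% confidence interval are also reported without patients who take folate-containing vitamins at baseline and decline to stop. Fix that status at enrolment, so that patients who agree to stop stay in and vitamins started later remove nobody. Add the status to the covariates.
4. In section 8.5, show the 30-patient percentage both ways.

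The cost is wording in four sections and one extra analysis with somewhat lower precision (exact power 73% with 54 non-users, 65% with 48). With few users, the covariate's coefficient will be imprecise and should be read as descriptive. Intake is already collected under section 5.5, so no new data are needed and enrolment stays at 75.

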5.5.1 Other concomitant treatment

Other medication other than that described above, which is considered necessary for the patient's safety and wellbeing, may be given at the discretion of the Investigator and recorded in the appropriate sections of the CRF.

In addition, any unplanned diagnostic, therapeutic or surgical procedure performed during the study period must be recorded in the CRF.

5.6 Dose modification

Dose Reductions

Clinical Study Protocol - 6
 Olaparib - ESR-18-13807

In case a dose reduction is necessary, the Study treatment will be administered as follows:

Table 4 Dose reductions for olaparib to manage adverse events

Initial Dose	Following re-challenge post interruption: Dose reduction 1	Dose reduction 2
300 mg twice daily	250 mg twice daily	200 mg twice daily
250 mg twice daily	200 mg twice daily	150 mg twice daily
200 mg twice daily	150 mg twice daily	100 mg twice daily

Table 5 Dose reduction for olaparib if patient develops moderate renal impairment

Initial Dose	Moderate renal impairment (calculated creatinine clearance by Cockcroft -Gault equation or based on a 24 hour urine test between 31 and 50 ml/min): Dose reduction
300 mg twice daily	200 mg twice daily

If starting dose is 200 mg twice daily, and patient develops renal impairment, dose modification will be determined by the treating physician.

Table 6 Dose reductions for olaparib if patient has to start taking a strong or moderate CYP3A inhibitor

Initial Dose	Strong CYP3A inhibitor	Moderate CYP3A inhibitor
300 mg twice daily	100 mg twice daily	150 mg twice daily

If starting dose is 200 mg twice daily, and patient is required to take a strong or moderate CYP3A inhibitor, dose modification will be determined by the treating physician.

For guidance on dose reductions for management of AEs (including renal impairment) refer to Section 8.4.4.

For guidance on dose reductions when concomitant strong or moderate CYP3A inhibitors cannot be avoided see Section 6.5.

When dose reduction is necessary patients will take one 150 mg tablet and one 100 mg tablet twice daily or two x 100 mg tablet twice daily (see Section 8.4.4), or one 150 mg tablet twice daily or one 100 mg tablet twice daily (see Section 6.5).

Folic Acid dose modification:

Clinical Study Protocol - 6
Olaparib - ESR-18-13807

Patients with folate deficiency will start folic acid supplementation at 1 mg daily. If they continue to have a Hgb less than 10 g/dl (grade 2) and folate deficiency despite folate supplementation, folic acid dose can be increased to 2 mg daily or higher at the discretion of the investigator.

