1. PROTOCOL SUMMARY

1.1 Schedule of Activities (SoA)

1. Participants will be screened for eligibility with medical history, physical exam, prior treatment, history of anemia and blood tests including baseline CBC, reticulocyte count, ferritin, B-12 and serum folate level
2. If inclusion criteria are met and after signing a consent form, participants will start olaparib 300 mg twice daily, commercially approved
3. Assessment of CBC/serum folate will occur every 2 weeks for the first 3 months and then monthly for a total of 6 months from the time of enrollment onto study therapy. If the patient develops folate deficiency and requires folate replacement, CBC/serum folate and reticulocyte count will occur every 2 weeks for 12 months.
4. One-time measurement of serum folate to occur one month after completion or discontinuation of therapy with olaparib
5. If folate deficiency is identified (defined as any level below normal) at any time point, the following parameters will be assessed in 2 weeks or at the next visit/assessment point: a repeat CBC/serum folate level along with B-12, LDH, reticulocyte count, methylmalonic acid, and homocysteine. These labs (CBC/serum folate level, B-12, LDH, reticulocyte count, methylmalonic acid, and homocysteine) need to be drawn once- 2 weeks after initial folate deficiency is identified for confirmation purposes and to rule out co-existing B-12 deficiency or other causes of anemia.
6. Once folate deficiency is confirmed in the setting of hemoglobin (Hgb) less than 12 g/dl but above 10.0 g/dl, patients will be randomized to folate supplementation or placebo. At that point, assessment of CBC/reticulocyte count and folate levels will continue every 2 weeks.
7. If Hgb is above 12.0 g/dl and no folate deficiency is identified, patients will not be randomized. Assessment of CBC/serum folate will continue every 2 weeks for the first 3 months and then monthly for a total of 6 months from the time of enrollment onto the study.
8. If folate deficiency is identified in setting of Hgb less than 10.0 g/dl, patients will not be randomized but will receive folic acid supplementation at 1 mg daily. These patients will have weekly assessments of CBC/reticulocyte count and folate levels until Hgb improves to a level above 10.0 g/dl. At that point, assessment of CBC/reticulocyte count and folate levels will change back to every 2 weeks. However, folic acid replacement will continue as initiated.

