3. STUDY DESIGN

3.1 Overall design

This is a pilot, multi-center study evaluating the prevalence and timing of folate deficiency in patients with advanced solid tumors who are eligible to receive olaparib.

If patients develop folate deficiency concomitantly with a Hgb less than 12.0 g/dl (grade 1), they will then be randomized to receive either a placebo or folate supplementation.

All randomized patients who develop a Hgb less than 10 g/dl (grade 2) concomitantly with folate deficiency will receive folic acid supplementation irrespective of their prior randomization. If such patients were originally randomized to receive folic acid and continue to have a Hgb less than 10 g/dl and folate deficiency despite folate supplementation, folic acid dose will be increased to 2 mg daily or higher at the discretion of the investigator.

Patients will continue with olaparib until objective disease progression (determined by treating physician assessment) as long as in the Investigator's opinion they are benefiting from treatment and they do not meet any other discontinuation criteria.

For an overview of the study design see Figure 1, Section 1.3. For details on treatments given during the study, see Section 5.1 Treatments Administered.

For details on what is included in the efficacy and safety endpoints, see Section 2 Objectives and Endpoints.

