7.4.4.1 Management of haematological toxicity

7.4.4.2 Management of anaemia

Table 8 Management of anaemia

Haemoglobin	Action to be taken
Hgb < 10 but ≥ 8 g/dl (CTCAE Grade 2)	
First occurrence: Give appropriate supportive treatment and investigate causality. Investigator judgement to continue olaparib with supportive treatment (e.g., transfusion) or interrupt dose for a maximum of 4 weeks. Study treatment can be restarted if Hb has recovered to > 9g/dl.
 
Subsequent occurrences: If Hgb < 10 but ≥ 9 g/dl investigator judgement to continue olaparib with supportive treatment (e.g., transfusion) or dose interrupt (for max of 4 weeks) and upon recovery dose reduction may be considered (to 250 mg twice daily as a first step and to 200 mg twice daily as a second step). If Hgb < 9 but ≥ 8 g/dl, dose interrupt (for max of 4 weeks) until Hb ≥ 9 g/dl and upon recovery dose reduction may be considered (to 250 mg twice daily as a first step and to 200 mg twice daily as a second step).

Hgb < 8 g/dl (CTCAE Grade 3)	
Give appropriate supportive treatment (e.g., transfusion) and investigate causality. Interrupt olaparib for a maximum of 4 weeks until improved to Hgb ≥ 9 g/dl. Upon recovery dose reduce to 250 mg twice daily as a first step and to 200 mg twice daily as a second step in the case of repeat Hgb decrease.

Common treatable causes of anemia (e.g., iron, vitamin B12 or folate deficiencies and hypothyroidism) should be investigated and appropriately managed. In some cases management of anemia may require blood transfusions. For cases where patients develop prolonged haematological toxicity (≥2 week interruption/delay in study treatment due to CTC grade 3 (Hgb less than 8.0 g/dl) or worse anemia and/or development of blood transfusion dependence), refer to guidance later in this section for the management of this.

Clinical Study Protocol - 6
Olaparib - ESR-18-13807

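### Section 5.6 starts folic acid in patients with folate deficiency without exception, which contradicts the randomisation of eligible deficient patients in Sections 1.1, 3.1 and 8.4.1

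*Combined protocol and SAP*

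**What the plan says.** Section 5.6, under its folic acid sub-heading, states: "Patients with folate deficiency will start folic acid supplementation at 1 mg daily". The next sentence deals with escalation: "If they continue to have a Hgb less than 10 g/dl (grade 2) and folate deficiency despite folate supplementation", the dose can be raised. Neither sentence mentions randomisation.

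Four other places govern the same decision:

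- Section 1.1, item 6: "Once folate deficiency is confirmed in the setting of hemoglobin (Hgb) less than 12 g/dl but above 10.0 g/dl, patients will be randomized". The two arms there are folate and placebo.
- Section 1.1, item 8, for deficiency with Hgb below 10 g/dl: "patients will not be randomized but will receive folic acid supplementation at 1 mg daily".
- Section 3.1, for deficiency with Hgb below 12 g/dl: "they will then be randomized to receive either a placebo or folate supplementation". The following paragraph gives folic acid to any randomised patient who is deficient with Hgb below 10 g/dl, whatever the allocation.
- Section 8.4.1: patients with deficiency and cytopenias up to grade 2 are "randomly assigned in a 1:1 ratio to receive folic acid supplementation 1 mg daily or no supplementation". Those with grade 3 or higher cytopenias receive folic acid and are not randomised.

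Below Table 8, Section 7.4.4.2 adds: "Common treatable causes of anemia (e.g., iron, vitamin B12 or folate deficiencies and hypothyroidism) should be investigated and appropriately managed".

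**The concern.** The subject of the 5.6 sentence is patients with folate deficiency, not patients assigned to folic acid. For a deficient patient with Hgb between 10 and 12 g/dl, a site that follows 5.6 gives folic acid, while a site that follows 1.1, 3.1 or 8.4.1 randomises and leaves about half without it. Nothing nearby corrects a literal reader: Table 1 lists only olaparib and folic acid, with folic acid prescribed by the provider, and Section 5.3 as shown gives no allocation procedure.

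Timing adds to the conflict. Section 1.1 items 5 and 6 call for a confirmatory sample two weeks after the first low folate and randomise only once deficiency is confirmed. Section 5.6 asks for no confirmation, so folic acid could start before that sample and before randomisation.

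At stake is the trial's only randomised comparison. It is the test of the second hypothesis in Section 8.1, that replacing folic acid mitigates olaparib's haematologic toxicity, and it also carries the randomised comparisons of response rate and PFS in 8.4.1.

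**Working it through.** **1. The rules side by side, for a folate-deficient patient**

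| Hgb (g/dl) | 1.1 | 3.1 | 8.4.1 | 5.6, read literally |
|---|---|---|---|---|
| 12 or above | Repeat panel and biweekly labs (item 5, Table 1.1.1 B); no treatment decision in the visible text | Not randomised | Randomised only if another cytopenia up to grade 2 is present | Folic acid |
| Above 10, below 12 | Randomised once confirmed (item 6) | Randomised | Randomised 1:1 | Folic acid |
| 8 to below 10 (grade 2 in Table 8) | Folic acid, not randomised (item 8) | Folic acid if already randomised; the entry rule (below 12) states no lower limit | Randomised 1:1 | Folic acid |
| Below 8 (grade 3 in Table 8) | Folic acid, not randomised (item 8) | As the row above | Folic acid, not randomised | Folic acid |

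The clear contradiction is the second row. In the third row 5.6 agrees with item 8 and with the crossover rule in 3.1, but not with 8.4.1. In the first row 5.6 is the only folic acid instruction in the visible text.

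**2. The plan's own sample size**

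Inputs from Section 8.2: expected rate 0.66, null rate 0.50, one-sided 0.05, power 80%, attrition 20%.

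- Normal approximation: n = [(1.645 × √(0.5 × 0.5) + 0.842 × √(0.66 × 0.34)) / 0.16]² = 58.2, so 59.
- Exact binomial: with n = 60 and rejection at 37 or more deficient patients, the one-sided error is 0.046 and power is 0.802.
- Attrition: 60 / 0.80 = 75.

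The stated 60 and 75 reproduce. They serve the deficiency rate. Section 5.6 acts only after a deficiency has been recorded, and Section 2 defines the primary endpoint by a level below 7 ng/mL within three months, with no confirmation. If deficiency in 5.6 means that threshold, neither the endpoint nor its sample size depends on 5.6.

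**3. Largest possible number of controls**

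- Enrolled: 0.66 × 75 = 49.5 deficient; 49.5 / 2 = 24.75, about 25 controls.
- Evaluable: 0.66 × 60 = 39.6 deficient; 39.6 / 2 = 19.8, about 20 controls.

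Both are upper bounds, because they take every deficient patient as randomisable. The documents do not give the share with Hgb between 10 and 12 g/dl. If it is assumed to be 25% to 75%, the evaluable set gives 39.6 × 0.25 / 2 = 4.95 to 39.6 × 0.75 / 2 = 14.85, about 5 to 15 per arm. If every site followed 5.6 literally, there would be no untreated controls.

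**4. Dilution if controls are treated**

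Let D be the true difference and c the fraction of allocated controls given folic acid, assuming that they get its full effect. The control arm moves by cD, so the intention-to-treat difference is D − cD = (1−c)D. Required sample size scales with 1/(1−c)². The last column is an illustration only: an assumed effect of 0.8 SD, 19.8 per arm, two-sided 0.05, power = Φ(0.8 × (1−c) × √(19.8/2) − 1.96).

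| c (assumed) | Difference retained | Sample size multiple | Power, illustration |
|---|---|---|---|
| 0 | 100% | 1.00 | 0.71 |
| 0.25 | 75% | 1.78 | 0.47 |
| 0.50 | 50% | 4.00 | 0.24 |
| 0.75 | 25% | 16.00 | 0.09 |

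The plan states no power for this comparison, so there is no plan figure to set against the last column.

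**The case against.** The best defence is context. The sentence sits under a dose modification heading, and its continuation speaks of patients who still have Hgb below 10 g/dl, a group that receives folic acid under item 8 or the 3.1 crossover anyway. It can therefore be read as the starting dose for those who are to be supplemented. Other sections fit that reading: item 3 of 1.1 refers to patients who need replacement, 5.4 has folate doses recorded only where applicable, and the secondary endpoints refer to patients who neither received nor required folic acid. This stands as a plausible reading, and probably the intended one. It does not remove the contradiction, because the sentence does not say so.

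A reader might infer more than the documents support:

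- That 5.6 empties the randomised comparison. That is the worst case, c = 1, and requires sites to disregard 1.1, 3.1 and 8.4.1.
- That all deficient patients should be randomised, so that 5.6 conflicts for all of them. Only an eligible subset is randomised.
- That 1.1 has no rule for deficiency with Hgb of 12 g/dl or above. It has monitoring; what is missing from the visible text is a treatment decision. Figure 1 could not be read for this check and may supply one.
- That treating those patients biases the contrast towards no effect. It happens before randomisation, so it reduces the number available and may alter who is randomised, but does not itself bias the comparison between arms.
- That the paragraph under Table 8 is a second, independent contradiction. The table's rows start below 10 g/dl, where 1.1 and 3.1 already give folic acid. It conflicts only under 8.4.1, which keeps grade 2 patients in the randomisation.

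It is also fair that this is a pilot with a secondary, unpowered randomised comparison, and that the 3.1 crossover will dilute the contrast whatever 5.6 says.

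**Conclusion.** The contradiction is real and confined to patients eligible for randomisation. Its direct effect, if 5.6 is applied literally to allocated controls, is attenuation of the randomised secondary comparisons to about (1-c) of their true size. The fraction c is an assumption; the documents give no basis for estimating it. Early starts, before confirmation or at Hgb of 12 g/dl or above, cost numbers in a comparison that could have as few as about 5 to 15 per arm under the assumed shares above and cannot exceed about 20 evaluable or 25 enrolled per arm at the 66% rate.

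This should be fixed. It is not a threat to the trial's main result, and context offers sites a reading that avoids the conflict.

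**What to change.** - In 5.6, say which patients the sentence covers, for instance by limiting it to those whom the protocol's allocation rule assigns to folic acid, and reconcile it with 1.1, 3.1 and 8.4.1.
- In 1.1, state the path for a deficient patient with Hgb of 12 g/dl or above, and whether folic acid may start before the confirmatory sample.
- As a supporting change, add to the paragraph under Table 8 a cross-reference saying how it applies to a randomised control, given that 1.1, 3.1 and 8.4.1 set different haemoglobin limits.

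Which clinical rule to adopt is for the sponsor; the point is that there should be one. The cost is two or three sentences in an amendment and a memo to sites, with no added patients or procedures and no change to the sample size.
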